Check contraindications, warnings, and precautions to vaccination	○						See Section 7.1.1 for details
Check criteria for temporary delay for enrollment and study intervention administration	○						See Section 5.5 for details

CONFIDENTIAL

219900 (RSV OA=ADJ-023)
Protocol Amendment 2 Final

Type of contact	Visit 1	Visit 2 ^a	Visit 3	Visit 4	Visit 5	Visit 6	Notes
Time points	Day 1	Visit 1 + 7-14 days	Visit 1 + 30-60 days	Visit 3 + 30-42 days	Visit 1 + 180-210 days	Visit 1 + 350-380 days	
Body temperature before study intervention administration	●						The location for measuring temperature will be oral or axillary (See Section 8.1.6). Fever is defined as temperature $\geq 38.0^{\circ}\text{C}/100.4^{\circ}\text{F}$, regardless of the location of measurement.
Study group and intervention number allocation	○						See Section 6.3 for details
Study intervention administration (including 30-minutes post-study intervention administration observation)	●						See Section 6.1 for details
Recording of administered study intervention number	●						See Section 6.3.3 for details
Safety assessments							
Provide post-vaccination diary cards	○						See Section 10.3.5.1 for details
Train participants on completion of diary cards	○						See Section 10.3.5.1 for details
Return of post-vaccination diary cards		○ ^c	○				See Section 10.3.5.1 for details
Verify and transcribe post-vaccination diary cards			●				See Section 10.3.5.1 for details
Targeted physical examination (as needed, SoC)		○	○	○	○	○	See Section 8.1.5 for details
Record concomitant medication/vaccination	●	●	●	●	●	●	See Section 6.9 for details
Record solicited administration site and systemic events (within 7 days post-study intervention administration)	●	●	●				See Section 10.3.5 for details
Record unsolicited AEs (within 30 days post-study intervention administration) ^d	●	●	●				See Section 10.3.5 for details
Record SAEs related to study participation or concurrent GSK medication/vaccine	●	●	●	●	●	●	See Section 10.3.5 for details

CONFIDENTIAL

219900 (RSV OA=ADJ-023)
Protocol Amendment 2 Final

Type of contact	Visit 1	Visit 2 ^a	Visit 3	Visit 4	Visit 5	Visit 6	Notes
Time points	Day 1	Visit 1 + 7-14 days	Visit 1 + 30-60 days	Visit 3 + 30-42 days	Visit 1 + 180-210 days	Visit 1 + 350-380 days	
Record: - All SAEs ^d - All pIMDs - Pregnancies - (S)AEs leading to withdrawal from the study - Intercurrent medical conditions	●	●	●	●	●	●	See Section 10.3.5 for details
Study conclusion						●	See Section 4.4 for details

Note: The double-line borders indicate the analyses which will be performed on all data (i.e., data that are as clean as possible) obtained up to these timepoints.

AE = Adverse event; AESI = Adverse event of specific interest; AF = Atrial fibrillation; CMI = Cell-mediated immunity; eCRF = electronic case report form; pIMDs = Potential immune-mediated diseases; RSV = Respiratory Syncytial Virus; SAE = Serious adverse event; SoC = Standard of care; WOCBP = Women of childbearing potential.

- is used to indicate a study procedure that requires documentation in the individual eCRF.
- is used to indicate a study procedure that does not require documentation in the individual eCRF.

^a Visit 2 is planned in the CMI subset of the study population (30% of the group population i.e., 38 participants in the group, at the designated CMI sites).

^b Vital signs, urine sample for pregnancy test and blood sampling for RSV neutralizing titers, CMI and CCI must be taken on the same day, prior to study intervention administration. If the study intervention administration is delayed by any reason, the vital signs and samples (both blood and urine) will need to be collected again on the day of study intervention administration, urine pregnancy test needs to be repeated, and the first blood sample will be destroyed.

^c Participants must bring their diary cards at this visit for review, and the same would be re-dispensed to them.

^d AF will be considered as AESI in this study and will be additionally reported in the AF follow-up questionnaire (electronic or paper) in eCRF. The collection of AF will be performed following the AE/SAE reporting periods. The reporting of non-serious AF will be performed according to the unsolicited AE reporting period. The reporting of AF meeting the SAE definition (serious AF) will be performed according to the SAE reporting period.

Under special circumstances, home visits may be conducted at the discretion of the investigator (Refer to Section 8 for details).

Table 4 Intervals between study visits for IC 1-dose group (RSV_IC_1)

Interval	Planned visit interval	Allowed interval range
Screening Visit → Visit 1	-7 days	-30 to -7 days
Visit 1 → Visit 2*	7 days	7 - 14 days
Visit 1 → Visit 3	30 days	30 - 60 days
Visit 3 → Visit 4	30 days	30 - 42 days
Visit 1 → Visit 5	180 days	180 - 210 days
Visit 1 → Visit 6	365 days	350 - 380 days

* Only in the CMI subset.

Table 5 Intervals between study visits for IC 2-dose group (RSV_IC_2)

Interval	Planned visit interval	Allowed interval range
Screening Visit → Visit 1	-7 days	-30 to -7 days
Visit 1 → Visit 2*	7 days	7 - 14 days
Visit 1 → Visit 3	30 days	30 - 60 days
Visit 3 → Visit 4	30 days	30 - 42 days
Visit 3 → Visit 5	180 days	180 - 210 days
Visit 3 → Visit 6	365 days	350 - 380 days

* Only in the CMI subset.

Table 6 Intervals between study visits for healthy participant group (RSV_HA)

Interval	Planned visit interval	Allowed interval range
Visit 1 → Visit 2*	7 days	7 - 14 days
Visit 1 → Visit 3	30 days	30 - 60 days
Visit 3 → Visit 4	30 days	30 - 42 days
Visit 1 → Visit 5	180 days	180 - 210 days
Visit 1 → Visit 6	365 days	350 - 380 days

* Only in the CMI subset.

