^f AF will be considered as AESI in this study and will be additionally reported in the AF follow-up questionnaire (electronic or paper) in eCRF. The collection of AF will be performed following the AE/SAE reporting periods. The reporting of non-serious AF will be performed according to the unsolicited AE reporting period. The reporting of AF meeting the SAE definition (serious AF) will be performed according to the SAE reporting period.

Under special circumstances, home visits may be conducted at the discretion of the investigator (Refer to Section [8](#) for details).

Table 2 Schedule of Activities for the IC 2-dose group (RSV_IC_2)

Type of contact	Screening Visit	Visit 1	Visit 2 ^a	Visit 3	Visit 4	Visit 5	Visit 6	Notes
Time points	-30 to -7 days	Day 1	Visit 1 + 7-14 days	Visit 1 + 30-60 days	Visit 3 + 30-42 days	Visit 3 + 180-210 days	Visit 3 + 350-380 days	
Baseline and demography assessments								
Informed consent	●							See Section 10.1.3 for details
Assignment/recording of participant number	●							See Section 6.3.1 for details
Check inclusion and exclusion criteria	●	●						See Sections 5.1 and 5.2 for details
Check with participants if he/she will appoint a caregiver, and distribute caregiver information letter to caregiver, when applicable	○	○	○	○	○	○	○	See Section 8 for details
Collect demographic data	●							See Section 8.1.1 for details
Record relevant medical history	●							See Section 8.1.2 for details
Record vaccination history	●							See Section 8.1.2 for details
Record specific transplant information	●							See Section 8.1.3 for details
Record height and weight	●							See Section 8.1.4 for details
History directed physical examination	○							See Section 8.1.5 for details
Record vital signs		● ^b		● ^b				See Section 8.1.6 for details
Screening conclusion	●							
Laboratory assessments								
Safety blood sample (Hematology & Biochemistry for liver and renal function; ~6 mL)	●							See Section 8.3.1 for details
Urine pregnancy test (if applicable, WOCBP only)	●	● ^b		● ^b				See Section 8.3.3 for details
Blood sampling (~ 8.5 mL) for RSV neutralizing titers		● ^b	●	● ^b	●	●	●	See Section 8.2 for details
Blood sampling (~ 30 mL) for CMI response (in CMI subset only)		● ^b	●	● ^b	●	●	●	See Section 8.2 for details
CCI								

CONFIDENTIAL

219900 (RSV OA=ADJ-023)
Protocol Amendment 2 Final

Type of contact	Screening Visit	Visit 1	Visit 2 ^a	Visit 3	Visit 4	Visit 5	Visit 6	Notes

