Record concomitant medication/vaccination	•	•	•	•	•	•	•	See Section 6.9 for details
Record solicited administration site and systemic events (within 7 days post-study intervention administration)		•	•	•	•			See Section 10.3.5 for details
Record unsolicited AEs (within 30 days post-study intervention administration) ^f		•	•	•	•			See Section 10.3.5 for details
Record SAEs related to study participation or concurrent GSK medication/vaccine	•	•	•	•	•	•	•	See Section 10.3.5 for details
Record: - All SAEs ^f - All pIMDs - Pregnancies - AESIs specific for renal/lung transplant - (S)AEs leading to withdrawal from the study - Intercurrent medical conditions		•	•	•	•	•	•	See Section 10.3.5 for details
Study conclusion							•	See Section 4.4 for details

Note: The double-line borders indicate the analyses which will be performed on all data (i.e., data that are as clean as possible) obtained up to these timepoints.

CONFIDENTIAL

219900 (RSV OA=ADJ-023)
Protocol Amendment 2 Final

AE = Adverse event; AESI = Adverse event of specific interest; AF = Atrial fibrillation; CMI = Cell-mediated immunity; eCRF = electronic case report form; eGFR = estimated glomerular filtration rate; FEV1 = forced expiratory volume in 1 second; LTx = Lung transplant; **CCI** [REDACTED]; pIMDs = Potential immune-mediated diseases; RSV = Respiratory Syncytial Virus; RTx = Renal transplant; SAE = Serious adverse event; SoC = Standard of care; TBBx = Transbronchial Biopsy; WOCBP = Women of childbearing potential.

- is used to indicate a study procedure that requires documentation in the individual eCRF.
- is used to indicate a study procedure that does not require documentation in the individual eCRF.

^a Visit 2 is planned in the CMI subset of the study population (30% of the group population i.e., 38 participants in the group, at the designated CMI sites).

^b Vital signs, urine sample for pregnancy test and blood sampling for RSV neutralizing titers, CMI and **CCI** [REDACTED] must be taken on the same day, prior to study intervention administration. If the study intervention administration is delayed by any reason, the vital signs and samples (both blood and urine) will need to be collected again on the day of study intervention administration, urine pregnancy test needs to be repeated, and the first blood sample will be destroyed.

^c Participants must bring their diary cards at this visit for review, and the same would be re-dispensed to them.

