5.5. Criteria for temporarily delaying enrollment/ administration of study intervention

Enrollment/study intervention administration may be postponed within the permitted visit interval until transient conditions cited below are resolved and before the end of recruitment period:

- Participants (SOT patients) with any clinically significant (in the opinion of the investigator) hematologic/biochemical values out of normal range which are expected to be temporary may be retested once at a later date within the allowed visit interval.
- Acute disease and/or fever at the time of study intervention administration. Refer to the SoA (Section 1.3) for definition of fever and preferred location for measuring temperature in this study.
- Participants with a minor illness (such as mild upper respiratory infection, mild diarrhea) without fever may be enrolled and/or dosed at the discretion of the investigator.
- In case of administration of vaccines, study intervention administration should be postponed, within given protocol timelines and prior to the end of the study enrollment period, to allow respect of at least 30 days interval between other vaccination and study intervention administration.
- In case of administration of inactivated, subunit and split influenza vaccines or COVID-19 vaccines (fully licensed or with EUA): postponement of study intervention administration within given protocol timelines and prior to the end of the study enrollment period, to allow respect of at least 14 days interval between flu/COVID-19 vaccination and study intervention administration.
- Participants with symptoms suggestive of active COVID-19 infection (e.g., fever, cough, etc.). The return of the participant to the site will follow the specific guidance from local public health and other competent authorities (e.g., free of symptoms, COVID-19 negative testing, etc.).

- Participants with known COVID-19 positive contacts may be dosed at least 14 days after the exposure, provided that the participant remains symptom-free, and at the discretion of the investigator.

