7. DISCONTINUATION OF STUDY INTERVENTION AND PARTICIPANT DISCONTINUATION/WITHDRAWAL

7.1. Discontinuation of study intervention

Discontinuation of study intervention refers to any participant who has not received all planned doses of the study intervention. In rare instances, it may be necessary for a participant to permanently discontinue study intervention. If study intervention is permanently discontinued, the participant should, if possible, continue other study procedures (e.g., safety or immunogenicity), planned in the study protocol at the discretion of the investigator.

The primary reason for premature discontinuation of the study intervention will be documented in the eCRF based on the list below:

Reasons	Additional items/Sub-reasons
AE	Unsolicited AE
	Solicited AE
	SAEs / pIMDs /AESIs
Lost to follow-up	
Withdrawal by Participant	Burden of Procedure
	Participant Relocated
	COVID-19

Reasons	Additional items/Sub-reasons
	Other, Specify
Investigator Decision	Specify
Protocol Deviation	Specify
Site Terminated by Sponsor	
Study Terminated by Sponsor	
Pregnancy	
Death	
Other	Specify

AE = Adverse event; AESI = Adverse event of special interest; COVID-19 = Coronavirus disease; pIMD = Potential immune-mediated disease; SAE = Serious adverse event.

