8.1.6. Vital signs

At minimum, temperature, vital signs (e.g., heart rate, respiratory rate, and blood pressure) will be recorded.

Vital signs are to be taken after at least 10 minutes of rest and before blood collection for laboratory tests (if applicable) and will consist of systolic/diastolic blood pressure, heart rate and respiratory rate by counting the number of breaths for 1 minute before vaccination at Visit 1 and Visit 3.

Blood pressure and pulse measurements will be assessed with a completely automated device. Manual techniques will be used only if an automated device is not available.

In case of increased blood pressure (i.e., systolic BP ≥ 140 mm Hg, and /or diastolic BP ≥ 90 mm Hg) the measurements of 3 consecutive blood pressure readings will be recorded at intervals of at least 1 minute. The average of the 3 blood pressure readings will be recorded [Smith, 2005].

Collected information needs to be recorded in the eCRF.

If the investigator determines that the participant's health on the day of study intervention administration temporarily precludes dosing, the visit will be rescheduled. Vital signs will be re-taken in case of delayed vaccination. Refer to the Section 5.5 for the list of criteria for temporary delay of study intervention administration.

The body temperature of each participant needs to be measured prior to study intervention administration and recorded in the eCRF. The location for measuring temperature will be oral or axillary. If the participant has fever (defined as temperature $\geq 38.0^{\circ}\text{C}/100.4^{\circ}\text{F}$ regardless of the location of measurement) on the day of study intervention administration, the visit will be rescheduled (refer to Section 5.5 for details).

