9.3.1. Primary endpoints/estimands analyses

The co-primary endpoints/estimands are described in Section 3. The primary analysis will be performed on the PPS.

MGI, i.e., the geometric mean of the within-participant ratios, of serum neutralizing titers against RSV-A and RSV-B post-Dose 2 (Visit 4) over post-Dose 1 (Visit 3) will be computed with their 95% CI in the RSV_IC_2 group.

CIs for MGI will be based on a back transformation of CI for the mean of the difference between log10-transformed values, assuming that log-transformed values are normally distributed with unknown variance.

Missing data will not be imputed.

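### Table 2 footnote b orders the first Visit 3 blood sample in RSV_IC_2 destroyed when dose 2 is delayed, without requiring a replacement, so a Visit 3 post-Dose 1 value can be lost in that arm alone

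*Protocol*

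**What the plan says.** Protocol Section 1.3, Table 2 (RSV_IC_2) has a row for "Blood sampling (~ 8.5 mL) for RSV neutralizing titers" and one for CMI blood. Both carry footnote b at Visit 1 and again at Visit 3. The trigger in the footnote is broad: "If the study intervention administration is delayed by any reason, the vital signs and samples (both blood and urine) will need to be collected". Re-collection is tied to the dosing day, and the footnote ends: "urine pregnancy test needs to be repeated, and the first blood sample will be destroyed". It makes no exception for Visit 3. Tables 1 and 3 (RSV_IC_1 and RSV_HA) attach footnote b to blood draws at Visit 1 only.

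Other sections bear on what the Visit 3 sample is for:

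- Section 8.2.3, Table 14 labels Visit 3 a post-dose-1 read-out for all participants.
- Section 9.3.2 uses Visit 3 for the GMT by group, the healthy over pooled-IC GMT ratio, the Visit 3 over Visit 1 MGI and CMI descriptives.
- Section 9.2, Table 20 defines contribution to the PPS by timepoint.
- Section 5.5: "Enrollment/study intervention administration may be postponed within the permitted visit interval until transient conditions cited below are resolved". For dose 2 the interval is Visit 1 + 30-60 days (Table 5).
- Section 7.1, on participants whose dosing is permanently discontinued: "the participant should, if possible, continue other study procedures (e.g., safety or immunogenicity".

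**The concern.** The rule suits a baseline sample. If dose 1 slips, a fresh pre-dose sample replaces a stale one and nothing of value is lost. At Visit 3 in RSV_IC_2 the same tube has two roles. It precedes dose 2, and it is the scheduled measurement of the response to dose 1. The second role does not need dose 2 to be given.

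The footnote ties re-collection to the dosing day but does not tie destruction to that day arriving. If dose 2 is postponed and then abandoned, the footnote calls for no redraw, while a valid in-window sample has been ordered destroyed. Destruction cannot be undone. The loss falls on one randomised arm and on participants whose dosing was delayed, for example by acute illness or a recent vaccination. In the other two groups a Visit 3 sample drawn on an equivalent day is not subject to this rule.

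**Working it through.** **1. Which analyses can lose data.** Take an RSV_IC_2 participant who has blood drawn at Visit 3, has dose 2 postponed, never receives it, and has no further draw within days 30-60.

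- Co-primary MGI. Section 9.3.1 specifies "post-Dose 2 (Visit 4) over post-Dose 1 (Visit 3) will be computed with their 95% CI in the RSV_IC_2 group". This participant has no post-Dose 2 value, so no ratio exists whatever happens to the tube. If dose 2 is given in window, the redraw supplies the denominator. No loss by this route.
- Secondary Visit 3 analyses (GMT, Visit 3 over Visit 1 MGI, healthy over pooled-IC ratio). The participant could contribute under the by-timepoint PPS, subject to the other PPS criteria. The value is lost.
- CMI at Visit 3. Lost if the participant is in the subset.

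**2. What other post-Dose 1 data remain.** Table 2 footnote a: "Visit 2 is planned in the CMI subset of the study population (30% of the group population i.e., 38 participants in the group". So 38/125 = 30.4% have a Visit 2 sample taken after Dose 1, and 87/125 = 69.6% do not (Table 9 gives the 38/87 split). Under Section 7.1, Visits 4 to 6 may still be sampled. What is lost is the Visit 3 timepoint value, not all post-Dose 1 information.

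**3. How many participants.** The documents give no rate. Assume 5-10% of 125 are delayed at Visit 3 and 25-50% of those are never dosed:

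- Delayed: 125 × 0.05 = 6.25 to 125 × 0.10 = 12.5.
- Never dosed: 6.25 × 0.25 = 1.6 to 12.5 × 0.50 = 6.3, so about 2 to 6.

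This makes no deduction for delays found before the draw or for redraws at a rescheduled visit, so it leans high. The allowance in Section 9.5 is 125 × 0.20 = 25 per group.

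**4. Effect on precision.** Section 9.5.1 states a detectable fold of 1.45 at 80% power for 200 pooled IC against 100 healthy participants, with 1-sided alpha 2.5% and SDs 0.50 and 0.45 on the log10 scale.

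- SE = √(0.45²/100 + 0.50²/200) = √(0.002025 + 0.001250) = 0.0572.
- Normal approximation: 10^((1.960 + 0.842) × 0.0572) = 1.447. The unequal-variance t calculation gives 1.449, which reproduces the stated 1.45.

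Removing k Visit 3 values from the 200, by the t calculation:

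| k lost | Detectable fold |
|---|---|
| 0 | 1.449 |
| 5 | 1.452 |
| 10 | 1.454 |
| 20 | 1.460 |

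The paired figure in Table 21 (SD 0.5, 80% power, n = 100) reproduces as 1.385 against the stated 1.39. By step 1, this rule does not change it.

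**The case against.** The strongest reply is that the footnote describes replacement. It speaks of dosing that is delayed, orders a second collection, and only then disposes of the first sample; calling it the first presupposes a second. Abandoned dosing is discontinuation, which Sections 7.1 and 7.1.1 cover. That is a fair reading, but the footnote does not state when destruction takes place or make it depend on the second draw, so sites or laboratories could act on it differently.

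Several limits on the concern stand in full:

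- Some delays are found before any blood is drawn. Section 8.1.6: "Vital signs are to be taken after at least 10 minutes of rest and before blood collection for laboratory tests (if applicable". Fever leads to rescheduling, and a recent vaccination can be established by asking.
- Sections 8.1.5 and 8.1.6 have the visit itself rescheduled, so an in-window draw may still take place even if dose 2 is then refused or contraindicated.
- Under Section 9.2.1 some of these participants may be removed from the PPS anyway, so not every retained sample would be analysed.
- A dosing-day redraw after day 60 already departs from Section 5.5, so it is not a consequence of the planned procedure.

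Two stronger readings are tempting. A reader might infer that the participant loses the only post-Dose 1 sample. Visit 2 in the subset and possible draws at Visits 4 to 6 contradict that. A reader might also infer that the co-primary MGIs are at risk, because Visit 3 is their denominator. Without dose 2 there is no numerator, so destroying the tube costs the primary analysis nothing.

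**Conclusion.** The point holds in a narrow form. Footnote b carries a baseline rule over to Visit 3 in RSV_IC_2 and leaves destruction unconditional. Followed literally, it can discard a valid in-window post-Dose 1 value that Table 14, the by-timepoint PPS and Section 7.1 all treat as worth having without dose 2. The harm is confined to one arm and to secondary Visit 3 analyses, including CMI in the subset.

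The size is probably a handful of participants, about 2 to 6 on assumed rates that the documents neither support nor exclude. The effect on precision is slight. The loss would be selective, since it follows delayed dosing, but no bias can be quantified from the documents and none is claimed here. The case for acting is that the loss is irreversible and costs very little to prevent.

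**What to change.** Restrict the unconditional destruction clause in Table 2 footnote b to Visit 1. For Visit 3 in RSV_IC_2, state three things:

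- The first in-window sample is kept until a valid in-window replacement has been drawn on the dosing day.
- Once that replacement exists, it is the Visit 3 value and the first sample may be destroyed.
- If no such replacement is drawn, the first sample is tested and used as the Visit 3 post-Dose 1 value.

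Samples from participants who withdraw from the study remain governed by Section 7.2.

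The cost is a revised footnote, one line in the laboratory manual and a few extra stored tubes. No visit or blood draw is added, and the rules for giving, delaying or withholding dose 2 do not change.
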